1.0 OBJECTIVES

Primary objective:

1. Determine the response rate (2008 IWCLL/NCI-WG criteria) to treatment with single-agent ofatumumab in previously untreated, early-stage, high-risk patients with CLL/SLL.

Secondary objectives:

1. Determine the time-to-progression for high-risk patients treated with ofatumumab.
2. Determine the time-to-next chemoimmunotherapy or alternative therapy.
3. Evaluate the pharmacokinetics of single-agent ofatumumab in high-risk, previously untreated patients with CLL/SLL.
4. Evaluate for circulating CD20⁺ cells through treatment and in follow-up in high-risk patients treated with ofatumumab.
5. Evaluate safety and toxicities of ofatumumab in previously untreated high-risk patients with CLL/SLL.

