Prior clinical trials demonstrated activity for rituximab in treating early-stage, treatment-naïve high-risk (β 2M \geq 3 mg/L) CLL⁶. The treatment was 8 weekly doses of rituximab 375mg/m². Patients were previously untreated, high-risk by elevated β 2M (\geq 3 mg/L). There were 34 patients enrolled and treated. The CR rate was 9%, nPR was 21%, and PR was 53% (ORR 82%). The median time to treatment failure (N=34) was 27 months and the median time to progression for responders (N=28) was 43 months. Responses and response duration will be compared to this historical trial. Time to first chemoimmunotherapy will be evaluated based on observed versus expected (O/E) ratio using the MDACC CLL database and multivariable models with nomograms developed to predict time to chemoimmunotherapy based in presenting characteristics. Given the activity and tolerability of ofatumumab, it is an ideal candidate to evaluate for single-agent activity in early-stage, high-risk patients with CLL.

The overall objective of this phase II study is to evaluate the efficacy of ofatumumab in treating high-risk, watch-and-wait, treatment-naïve patients with CLL/SLL to delay time to first chemoimmunotherapy treatment. For this clinical trial, patients will be defined as high-risk for progression based on the presence of one of the following: Rai stage II, serum beta-2 microglobulin (β 2M) of \geq 3 mg/L, absolute lymphocyte count \geq 25,000/ μ L, unmutated (\leq 2%) *IGHV* gene or mutated *IGHV3-21*, ZAP70 positive, CD38 positive (\geq 30%), or 11q or 17p deletion by FISH.

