4.0 PATIENT ELIGIBILITY

4.1 Inclusion criteria:

1. Diagnosis of chronic lymphocytic leukemia (CLL) / small lymphocytic lymphoma (SLL), previously untreated, Rai stage 0-II
2. At least 1 of the following high-risk features for previously untreated patients:
 - Rai stage II disease
 - Rai stage 0-I with disease-related fatigue
 - Serum β 2M \geq 3 mg/L
 - Absolute lymphocyte count \geq 25,000/ μ L
 - Unmutated *IGHV* gene or *IGHV3-21*
 - ZAP70 positive (\geq 20% by flow cytometry or positive by immunohistochemistry)
 - CD38 positive (\geq 30% by flow cytometry)
 - Deletion 11q or 17p by FISH
3. ECOG PS \leq 2
4. Age \geq 18 years
5. Patients must have adequate renal and hepatic function (creatinine <2 mg/dL, total bilirubin <2 mg/dL). Patients with renal or liver dysfunction due to organ infiltration with CLL/SLL may be eligible after discussion with the study chairman
6. Provide informed consent
7. Female patients (including those <1 year post-menopausal) and male patients who have not undergone previous surgical sterilization must agree to use contraception.

4.2 Exclusion Criteria:

1. Presence of 2008 IWCLL/NCI-WG indication for CLL treatment:
 - Constitutional symptoms related to CLL/SLL:
 - Fever $> 100.5^{\circ}\text{F}$ for \geq 2 weeks or night sweats for > 1 mo, both without evidence of infection
 - Unintentional weight loss of $\geq 10\%$ body weight in previous 6 months
 - Extreme fatigue (ECOG PS > 2 ; inability to work or perform usual activities)
 - Lymphocyte doubling time of ≤ 6 months or 50% increase in absolute lymphocyte count within 2 months
 - Progressive anemia (Rai stage III) or thrombocytopenia (Rai stage IV)
 - Recurrent infections unrelated to hypogammaglobulinemia
 - Autoimmune phenomenon poorly responsive to corticosteroids or other standard therapy
 - Massive, progressive or symptomatic lymphadenopathy (> 10 cm in longest diameter) or splenomegaly (> 6 cm below left costal margin)
2. Prior or concurrent chemotherapy, radiotherapy, or immunotherapy for CLL

3. Active infection (febrile and requiring IV/PO antibiotics) including hepatitis C or HIV, or significant medical illness including renal, cardiac, pulmonary disease, or current active hepatic or biliary disease (with exception of patients with Gilbert's syndrome, asymptomatic gallstones, liver metastases or stable chronic liver disease per investigator assessment)

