7.0 EVALUATION DURING STUDY

- 7.1 Monitoring during treatment will consist of weekly (\pm 3 days) blood counts and chemistries (through C1D50), then every 3 months (\pm 2 weeks) during follow-up until alternative treatment for CLL/SLL or death, whichever occurs first. A physician will see patients at least monthly (\pm 5 days) during treatment. A mid-level provider may evaluate patients weekly (\pm 2 days) during treatment (8 weeks) when not seen by the physician.
- 7.2 Follow-up visits will include PE with vital signs, interval history, toxicity/adverse event assessment, CBC with differential, and SMA12. Bone marrow examinations (aspirate, biopsy, and MRD evaluation) will be done at response

assessment (at least 2 months after last dose of ofatumumab) to confirm complete remission, then annually.

- 7.3 Patients will be followed at MDACC for all visits including follow-up, response assessment 3 months after the last ofatumumab dose, and at least annually. Patients will be considered off study when they start alternative treatment for their CLL.
- 7.4 For patients who are HBsAg⁻, HBcAb⁺, HBsAb^{+/-}, and HBV DNA⁻ on enrollment and who proceeded with treatment, HBV DNA PCR testing will be done every 2 months while on treatment, then every 3 months during follow-up for 6 months. Consult with a physician experienced in care and management of subjects with hepatitis B to manage/treat subjects who are anti-HBc positive. Initiate anti-viral therapy if required. If a subject's HBV DNA becomes positive during the study, notify the GSK medical monitor. For subjects who have not completed planned ofatumumab therapy, discuss with the medical monitor the risks and benefits of continuing or discontinuing ofatumumab before appropriate treatment decisions are made for that individual subject.
- 7.5 Information regarding concomitant medications will not be collected for patients on this study. This information is routinely collected and recorded as part of the patient's electronic record. If there is a need to refer to this, it will be available.

The schedule of events is detailed in Table 4.

Table 4. Schedule of Events

Test and Evaluations	Screening Visit Day ≤ -21	C1 D1	C1 D8	C1 D15	C1 D22	C1 D29	C1 D36	C1 D43	C1 D50 (EOT)	C1 D140	FU Q3 MO	ANNUAL FU
Informed consent	X											
Medical history	X											
Interval history, including adverse events and toxicity		X	X ^a	X ^b	X ^c	X ^c						
PE including VS	X	X	X ^a	X ^b	X ^c	X ^c						
Pregnancy test	X											

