β2 Microglobulin	X											
Screening BM asp/bx ^d	X											
Zap70, CD38, CD49d, thymidine kinase ^e , IGHV , FISH (13q del, +12, 11q del, and 17p del); and p53 expression ^d		X										
Staging CT of chest, abdomen, pelvis (Day ≤-2 mo)	X											
Hepatitis B surface Ag and surface and core Ab serology	X											
CBC with diff, PLT	X	X	X ^a	X ^b	X ^c	X ^c						
SMA 12	X	X	X ^a	X ^b	X ^c	X ^c						
Ofatumumab		X	X ^a									
For Pts HBsAg ⁻ , HBcAb ⁺ , HBsAb ⁺⁻ , HBV DNA ⁻ on enrollment, HBV DNA PCR testing will be done		X								X ^a	X ^b	X ^c
PK & PD, optional samples	X	X	X ^a	X ^b	X ^c	X ^c						
Response assessment (IWCLL criteria, staging CT scan, and BM for MRD)										X ^b		X ^c

BM=bone marrow evaluation; C=course; D=day; EOT=end of treatment; FU=follow-up; MO=months; PE=physical examination; VS=vital signs; CBC=complete blood count; PK=pharmacokinetic; PD=pharmacodynamic; IWCLL=International Working Group for CLL; MRD=minimal residual disease; ^aindicates ± 3 days; ^bindicates ± 2 weeks; ^cindicates ± 4 weeks; ^dif bone marrow evaluation is done within 3 months of enrollment, this will not need to be repeated. In these cases, if there is any prognostic factor information missing, this can be obtained by blood. If *IGHV* mutation status and ZAP70 were previously determined at any time, they do not need to be repeated. ^ewhen testing is available at MDACC.

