8.0 RESPONSE CRITERIA AND TOXICITY EVALUATION

Responses will be assessed according to the 2008 IWCLL guidelines (Table 5)⁷ at MDACC. Responses will be evaluated by physical examination; CBC; CT of chest, abdomen, pelvis; and for individuals in complete remission bone marrow aspirate and biopsy with evaluation of residual disease (MRD) by 4-color flow cytometry at least 3 months after completing ofatumumab.

Table 5. 2008 IWCLL Response Assessment

SITE	CR	PR
Nodes*†	None > 1.5 cm	Decrease ≥ 50%
Liver/Spleen	Not palpable	Decrease ≥ 50%
Symptoms	None	N/A
PMN	>1,500/µL	N/A
Platelet count	> 100,000/µL	>100,000/µL or increase ≥ 50% over baseline
Hemoglobin (untransfused)	>11.0 g/dL	>11.0 g/dL or increase ≥ 50% over baseline
Blood Lymphocytes	<4,000/µL	Decrease ≥ 50%
Bone Marrow Aspirate**	Normocellular <30% lymphocytes	> 50% decrease in marrow infiltrate or B lymphoid nodules
Biopsy	No lymphocyte infiltrate or nodules	

* CT scan of neck, chest, abdomen, and pelvis to confirm CR is recommended.

† Sum of the product of multiple lymph nodes.

** Evaluation for MRD will be performed either by 4-color flow cytometry or by molecular evaluation.

N/A=not applicable

Non-hematologic toxicity will be assessed, summarized and graded according to the Common Terminology Criteria for Adverse Events (CTCAE) Version 4.0. Hematologic toxicity will be assessed, summarized and graded according to the 2008 IWCLL Guidelines (Table 6).

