9.0 REMOVAL FROM STUDY

9.1 Progressive or Relapsed Disease

Progressive disease (PD) will be characterized by at least one of the following:

- $\geq 50\%$ increase in the sum of the products of at least two nodes or appearance of new palpable lymph nodes noted on two consecutive examinations at least two weeks apart (at least one node must be ≥ 2 cm).
- $\geq 50\%$ increase in the size of liver and/or spleen as determined by measurement below the respective costal margin; appearance of palpable hepatomegaly or splenomegaly which was not previously present.
- $\geq 50\%$ increase in absolute number of circulating lymphocytes over baseline with $\geq 5,000$ B cells/ μL .
- Transformation to a more aggressive histology (Richter syndrome) documented with biopsy.
- PLT or HGB decrease $\geq 50\%$ from baseline secondary to CLL/SLL.

9.2 Active HBV infection or hepatitis.

9.3 Patient request.

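### Does the undefined baseline in section 9.1's lymphocyte rule leave time-to-progression unusable?

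*Combined protocol and SAP*

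**What the plan says.** Secondary objective 1 in section 1.0 reads "Determine the time-to-progression for high-risk patients treated with ofatumumab". Section 2.0 reports a median time to progression of 43 months among the 28 responders in the earlier rituximab trial and adds: "Responses and response duration will be compared to this historical trial".

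The only progression criteria written out are in section 9.1, headed for progressive or relapsed disease, where any one bullet is enough. The lymphocyte bullet asks for a 50% or greater "increase in absolute number of circulating lymphocytes over baseline with" at least 5,000 B cells/µL. The node and liver/spleen increase clauses state no reference value.

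Section 8.0 says "Responses will be assessed according to the 2008 IWCLL guidelines (Table 5"), and that table covers complete response (CR) and partial response (PR) only. Table 4 has a row for "Response assessment (IWCLL criteria, staging CT scan, and BM for MRD"). Section 10.0 plans Kaplan-Meier estimates of overall and event-free survival and does not mention TTP.

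Under section 7.1, blood counts run every 3 months "during follow-up until alternative treatment for CLL/SLL or death, whichever occurs first".

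**The concern.** The word baseline carries the event date for a relapse that shows first in blood, and the plan does not say which value it is. Read as the pretreatment count, a full return to that count is a 0% increase. A patient could respond, lose the whole response in the blood and still have no lymphocyte event until the count rose another 50%. Read as the lowest count on study, the same patient would have had an event much earlier. Two analysts could date one relapse differently and both claim to follow the plan.

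At stake are TTP as a secondary endpoint and the planned comparison of response duration with the rituximab trial. A late event date would flatter ofatumumab if the earlier trial had counted from a lower reference.

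**Working it through.** **Which reading the text supports.** Table 5 uses an increase over baseline for platelets and hemoglobin at response, where only the pretreatment value makes sense. Table 6 grades falls from the pretreatment value, and its hemoglobin footnote contrasts baseline with subsequent measurements. Section 9.1 uses the same word for its platelet and hemoglobin falls. Nothing in the documents points to the lowest on-study value.

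**Inputs.** The 50% rise and the 5,000 B-cell floor come from section 9.1. The blood lymphocyte limits come from Table 5: below 4,000/µL for CR and a fall of at least 50% for PR. The worked pretreatment count of 25,000/µL is one of the entry features in section 4.1, under "At least 1 of the following high-risk features for previously untreated patients". The counts of 10,000 and 5,000 are illustrative. Every lymphocyte is first treated as a B cell.

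**Formulas.** B is the pretreatment count and N the lowest later count.
- Pretreatment reference: event at max(1.5 × B, 5,000).
- Lowest-value reference: event at max(1.5 × min(N, B), 5,000).
- Gap in doublings = log2(first ÷ second).

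| B | N | Pretreatment trigger | Lowest-value trigger | Gap (doublings) |
|---|---|---|---|---|
| 25,000 | 12,500 (PR limit) | 37,500 | 18,750 | 1.00 |
| 25,000 | 3,999 | 37,500 | 5,998.5 | 2.64 |
| 25,000 | 1,000 | 37,500 | 5,000 | 2.91 |
| 10,000 | 5,000 (PR limit) | 15,000 | 7,500 | 1.00 |
| 10,000 | 1,000 | 15,000 | 5,000 | 1.58 |
| 5,000 | 2,500 (PR limit) | 7,500 | 5,000 | 0.58 |

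On the pretreatment reading, the event at B = 25,000 lies log2(37,500 ÷ 25,000) = 0.58 doubling past full return. The two readings agree when 1.5 × B ≤ 5,000, that is B ≤ 3,333, or when the count never fell. If 2,000 of the lymphocytes are assumed not to be B cells, the floor becomes a total count of 7,000. The gap from a CR-level count at B = 25,000 is then log2(37,500 ÷ 7,000) = 2.42.

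**From doublings to months.** This needs a doubling time after treatment, which the documents do not give. Assumed values of 6, 12 and 24 months make the one-doubling gap 6, 12 and 24 months. The first sits on the section 4.2 exclusion limit at entry. How often relapse shows first in blood is also not given, so none of this converts to a change in median TTP.

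**What the lowest-value rule would do.**
- It calls progression inside the Table 5 PR lymphocyte limit whenever 1.5 × N < 0.5 × B, that is N < B ÷ 3. At B = 25,000 this means any lowest count under about 8,333. With N = 1,000 it fires at 5,000, which is 1 − 5,000 ÷ 25,000 = 80% below pretreatment.
- At 37,500 the B-cell floor needs 5,000 ÷ 37,500 = 13% of lymphocytes to be B cells. At 6,000 it needs 5,000 ÷ 6,000 = 83%, which a routine blood count cannot establish. Section 11.0 schedules B-cell counts only to 6 months of follow-up, and the Table 4 row that might extend them is headed "PK & PD, optional samples".

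**The plan's own efficacy figures.** The Simon rule (stop at 1 or fewer of 25; ineffective at 6 or fewer of 44) gives an early-termination probability of 0.329 at a 9% CR rate, against 0.33 stated. The type I error is 0.095, within 0.10, and power at 20% is 0.800. These reproduce and rest on CR alone.

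**The case for a change.** The strongest case for a change is that TTP is the first secondary objective and is to be set beside a published median. A citation of IWCLL criteria does not settle the reference value, because section 8.0 ties them to a table with no progression column and section 9.1 writes its own rule. Other bullets will catch some relapses, but the node and organ clauses are silent on their reference too. A definition paragraph would cost little.

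The textual points stand: baseline is undefined and section 10.0 names no TTP event. What they show is missing detail that has an evident answer. An analyst would take section 9.1 as the TTP event and the pretreatment value as baseline, and would say so in the report.

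The only substantive change would be to move the reference to the lowest value, and that is a trade-off. It lets one low weekly on-treatment count set the reference for good, and it creates a second progression definition beside the one used for removal. It may also reduce comparability with the rituximab trial, whose definition the documents do not give. Nor can its early firing be dismissed as rare by pointing to the 9–20% CR rates in the design. A count under 4,000 is only one row of the CR definition, and partial responders can reach it.

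**Conclusion.** No change to the plan follows. The wording leaves a gap, and the text itself supplies a sensible way to fill it. On the pretreatment reading, a blood-only relapse is dated once the count is 50% above its pretreatment value (37,500/µL at 25,000). That is one doubling later than a lowest-value rule would date it after a minimal partial response, and 2.6 to 2.9 doublings later after a CR-level count. These figures treat all lymphocytes as B cells and apply only when no other section 9.1 bullet is met first.

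The effect on median TTP, and the direction of any bias against the historical 43 months, cannot be determined from the documents. The CR endpoint, the Simon design and time to next therapy do not depend on this bullet.

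This rests on reading baseline as pretreatment, which Tables 5 and 6 support but no sentence states. If the sponsor meant another value, the dates of blood-led events would move, while the conclusions on CR would not.

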10.0 STATISTICAL CONSIDERATIONS

This is a phase II, open label, single-arm study. Sample size calculation will be based on the CR rate. The objective is to demonstrate a 20% CR rate for patients treated with single-agent ofatumumab. A CR rate of 9% was achieved in a previous phase II clinical trial with single-agent rituximab in a similar patient population. Simon's two-stage MinMax design will be used to assess efficacy in this study. In particular, a sample size of 44 is chosen to differentiate between a good response rate of 20% and a poor response rate of 9% at the significance level of 0.10 with 80% power. In particular, 25 patients will be enrolled at the first stage. If there is 1 or fewer responders among 25, the trial will be terminated due to lack of efficacy; otherwise an additional 19 patients will be treated resulting in a total of 44 patients. If there are 6 or fewer responses among 44 patients, the treatment will be concluded ineffective. The probability of early termination due to futility is 0.33.

The probability of toxicity will be monitored based on a beta-binomial model, assuming a priori that $p = \text{Prob}(\text{toxicity}) \sim \text{beta}(1, 1)$. The trial will be terminated if $\text{Prob}(p > .15 | \text{data}) \geq .9$. This rule will stop the trial if $[\#\text{patients with toxicity}] / [\#\text{patients evaluated}] \geq 3/7, 4/12, 5/17, 6/22, 7/27, 8/32, 9/37, \text{ or } 10/42$. The operating characteristics for toxicity are summarized in Table 7.

Table 7. Operating characteristics based on 1000 simulation study

true Prob(tox)	Pr(stop)	Median # Pts (25%, 75%)
0.05	0.004	44 (44, 44)
0.10	0.07	44 (44, 44)
0.15	0.25	44 (44, 44)
0.20	0.49	44 (12, 44)
0.30	0.89	12 (7, 22)
0.40	0.99	7 (7, 12)

Toxicity events, for purposes of safety monitoring, will be defined as ofatumumab-related grade ≥ 4 toxicity by CTCAE V 4.0 that persist longer than 1 week despite holding drug and/or dose reduction.

Descriptive statistical analysis will be used to explore the data, including histograms or box-plots, proportions, means, standard deviations. The Fisher's exact test or Chi-square test will be used for the univariable analysis on categorical variables (response variable with Yes versus No, for example). The t-test or Wilcoxon test will be used for continuous variables. The Kaplan-Meier survival analysis will be performed to estimate the overall survival and event-free-survival. The log-rank test will be used to assess the difference of survival functions between two groups. Toxicity will be reported by type, frequency and severity.

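### The declared primary endpoint (IWCLL response rate, category not given) is not the endpoint that carries the formal efficacy conclusion (CR rate)

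*Combined protocol and SAP*

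**What the plan says.** Section 1.0 (Objectives) lists a single primary objective: "Determine the response rate (2008 IWCLL/NCI-WG criteria) to treatment with single-agent ofatumumab" in the target population. It does not say whether response means CR alone or CR and PR together. CR appears in none of the five secondary objectives either.

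Section 10.0 (Statistical Considerations) says "Sample size calculation will be based on the CR rate" and then "The objective is to demonstrate a 20% CR rate for patients treated with single-agent ofatumumab". It takes the 9% null rate from the CR rate in the earlier rituximab trial. The terms then change within the same paragraph:

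- The 44 patients are to "differentiate between a good response rate of 20% and a poor response rate of 9" percent.
- First stage: "If there is 1 or fewer responders among 25, the trial will be terminated due to lack of efficacy".
- Final analysis: "If there are 6 or fewer responses among 44 patients, the treatment will be concluded ineffective".
- Operating characteristic given for the first stage: "The probability of early termination due to futility is 0.33".

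Section 2.0 (Background) gives the rituximab results in 34 patients as CR 9%, nPR 21%, PR 53% and overall response 82%. There the word responders covers all three categories: "the median time to progression for responders (N=28) was 43 months". Table 5 in Section 8.0 sets out criteria for both CR and PR.

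**The concern.** The result that carries the formal conclusion should also be the declared primary result. Here Section 1.0 points to an unspecified response rate and Section 10.0 to the CR rate, and only the latter has a null rate, a target rate and a decision rule. For overall response the plan offers only a general intention, in Section 2.0, to compare responses with the historical trial, and a list of descriptive summaries in Section 10.0.

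An author could therefore choose the headline endpoint after seeing the data and cite the protocol for either choice. The two candidates are far apart: in the historical trial the overall response rate was about nine times the CR rate (82/9 = 9.1).

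**Working it through.** **1. Inputs.** From Section 10.0: p0 = 0.09, p1 = 0.20, stop at ≤1 of 25, ineffective at ≤6 of 44, significance level 0.10, power 80%, early-termination probability 0.33. From Section 2.0: 34 historical patients, 28 of them responders, CR 9%, nPR 21%, PR 53%, overall response 82%.

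**2. Reproducing the stated design, with responder read as CR.**

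Probability of early termination at 9%:

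P(X ≤ 1 | n = 25, p = 0.09) = 0.91^25 + 25 × 0.09 × 0.91^24 = 0.0946 + 0.2340 = 0.3286 (stated 0.33).

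Probability of concluding activity, with X1 ~ Bin(25, p) and X2 ~ Bin(19, p):

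P(go) = Σ over x from 2 to 25 of P(X1 = x) × P(X2 ≥ 7 − x).

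| True CR rate | P(stop at stage 1) | P(go) | Meaning |
|---|---|---|---|
| 0.09 | 0.3286 | 0.0953 | type I error, limit 0.10 |
| 0.20 | 0.0274 | 0.8003 | power, target 0.80 |

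Expected sample size at 9%: 25 + 19 × (1 − 0.3286) = 37.8. A search over two-stage designs from n = 30 upward found none below n = 44 that meets both limits. At n = 44, the design 1/25, 6/44 has the smallest expected sample size under the null. The minimax claim is confirmed.

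This agreement shows that the arithmetic is right. It does not identify the endpoint, because the early-termination probability depends only on the 9% null and the 1-of-25 rule. What identifies CR is the text: the two opening sentences of Section 10.0, and the source of the 9%.

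**3. What responders means elsewhere.** The Section 2.0 percentages correspond to 3/34 = 8.8% CR, 7/34 = 20.6% nPR and 18/34 = 52.9% PR. 3 + 7 + 18 = 28, and 28/34 = 82.4%. So the 28 responders of Section 2.0 are CR + nPR + PR, whereas the responders of Section 10.0 are CRs only.

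**4. How the two sections can give different primary results.** Assumed counts, for illustration: 44 patients treated, at least 2 CRs among the first 25 so that the trial continues, 5 CRs in total, and 36 overall responses including those 5.

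- Under Section 10.0: 5 ≤ 6, so the conclusion is ineffective (CR rate 5/44 = 11.4%).
- Under Section 1.0 read as overall response: 36/44 = 81.8%, exact (Clopper–Pearson) 95% CI 67.3% to 91.8%.

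The 36 is the count nearest to the historical 82%. Both reports would follow the protocol.

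**The case against.** The strongest reply is that the two sections do not exclude each other. CR is one category of IWCLL response, and sizing a trial on one category of a broader objective is legitimate. Section 10.0 also explains itself: it names the CR rate twice, cites the historical CR rate of 9%, and then reuses the same 9% and 20%. Nobody applying the rule would be misled, so what remains could be called copy-editing.

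Much of this stands. In context the decision rule is clear, and the loose use of responders and responses would be minor on its own. A reader might go further and infer that the 1-of-25 and 6-of-44 rules count partial responses too, so that they could hardly ever stop the trial, or that the sample size is wrong. The documents do not support either inference. The opening of Section 10.0 ties the rule to CR, and on that reading the design meets its stated error rates.

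The reply does not settle what Section 1.0 means. Inferring CR in Section 10.0 leaves the declared primary objective without a category. Section 10.0 also does more than size the trial on CR: it states an objective of its own and attaches the verdict of ineffectiveness to it.

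**Conclusion.** Wrong as written: the primary endpoint is inconsistent between Sections 1.0 and 10.0. The design itself is sound for CR (early termination 0.329, type I error 0.095, power 0.800), and nothing here calls the sample size or cut-offs into question.

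What is at stake is which result is reported as primary. In the example above, the same data give a formally ineffective drug with an 11.4% CR rate, or an 82% response rate presented as primary. Those counts are assumed, chosen to match the historical overall response rate; they show that the conflict is possible, not how likely it is. The point should be fixed, and wording alone can do it.

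**What to change.** - **Section 1.0:** name the CR rate by 2008 IWCLL criteria as the primary endpoint. List the overall (CR or PR) response rate as a secondary endpoint.
- **Section 10.0:** in the hypotheses and in the 1-of-25 and 6-of-44 rules, replace the general response terms with *CR rate*, *complete responders* and *CRs*. Add one sentence saying that the overall response rate will be reported with an exact 95% CI.

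The cost is a wording amendment. The 44 patients, the cut-offs and the study procedures stay as they are. The small downside is that a high overall response rate can no longer be presented as the primary result.
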